5.3. Duration of Therapy

Treatment is planned for a total of 12 cycles of therapy and will continue until one of the following occurs:

1. Disease relapse
2. Serious illness that prevents further administration of treatment (i.e., progressive infection not responding to appropriate antibacterial and/or anti-fungal therapies)
3. Unacceptable adverse event(s)

4. Elective withdrawal of consent by the patient
5. Determination by the physician that it is no longer in the patient's best interest to continue on trial
6. Delay of the study drug dose for more than 56 days from the first day of the most recent cycle due to unresolved toxicities
7. Inability to tolerate either study drug at the lowest allowable dose levels
8. Initiation of breast feeding by the patient.
9. Patient pregnancy

All subsequent cycles may be initiated no sooner than 28 days and no later than 56 days from Day 1 of the previous cycle.

5.4. Duration of Follow-up

Patients will be followed for relapse and death for three years from the first day of the first cycle of treatment. Patients are routinely followed and monitored by JH physicians after SCT or chemotherapy, and patients who complete the study and continue to receive their care at JH will have survival captured annually at least.

5.5. Supportive Care Guidelines

Supportive care, including infection management and transfusion support, will follow good medical practice and institutional standard guidelines.

5.6. Study Parameters

The studies planned during the patient evaluation and therapy are listed in Table 4. This represents the basic follow-up plan and this will change for a change in patient condition. Patients will be requested to maintain a diary documenting administration of drug and any symptomatology. All attempts will be made to collect all the correlative studies, however, due to laboratory constraints (weekends, holidays, laboratory emergencies or staffing difficulties) and patient constraints (related to intercurrent illnesses, transportation, or inadequate sample), some samples will not be collected or will not be suitable for evaluation. A patient will be considered suitable for evaluation independent of the availability of correlative study material. A variation, of +/- 3 days from any weekly scheduled testing and +/- 7 days for all other study visits, is permitted.

Table 4

Parameter	Pre-treatment¹	Weekly during first cycle	Day 1 of each cycle	End of Treatment
History/Physical	X		X	X
Weight	X		X	X
Performance Status	X		X	X
CBC with Differential	X	X	X	X
PT, PTT	X			
Reticulocyte Count	X			X
Comprehensive Metabolic Panel	X	X	X	X
Phosphate	X		X	X
Magnesium	X		X	X
Toxicity Notation	X	X	X	X
EKG	X			
Review diary	X		X	X
Serum HCG for applicable women only	X			

¹ Within 14 days prior to enrollment.

6. Treatment Evaluation

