2.9. Clinical Studies with Differentiating Agents and GM-CSF

Our group has built upon such preclinical data and has focused on studying numerous agents with differentiating properties. A phase I trial of the differentiating agent Bryostatins with GM-CSF demonstrated clinical activity in refractory myeloid malignancies but was intolerable at biologically active doses.⁵¹ Subsequently, a Phase I study with MS-275 showed clinical activity and evidence of differentiation.⁴⁵ In a Phase II study of MS-275 and GM-CSF in patients with high-risk MDS or relapsed and refractory AML, 21% of patients achieved a response and demonstrated clinical evidence of differentiation.⁵² We propose a phase II study to determine the impact of maintenance therapy with 5-azacytidine and GM-CSF in patients with poor-risk AML or MDS, who are in remission after definitive treatment with either stem cell transplant or consolidation chemotherapy.

In order to precede relapse and to avoid lead time bias, treatment would need to commence within 185 days of definitive therapy. Furthermore, approximately 50% of relapses occur within the first year and up to 80% within two years after SCT, therefore we would limit the duration of maintenance therapy to one year, followed by two years of follow-up.

3. Patient Selection and Enrollment

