3.6. Informed Consent

All patients eligible for the study must be evaluated by one of the study investigators. Informed consent must be obtained and the consent form signed. A Johns Hopkins On-Study Form will be completed following fulfillment of the on-study requirements for laboratory work and eligibility criteria. For enrollment of non-English-speaking candidates, the policies and procedures mandated by the JH IRB will be followed as listed at the following website: <https://irb.jhmi.edu/Guidelines/nonenglishconsent.html>

4. Pretreatment Plan

A complete history and physical examination and list of medications will be documented for each patient within two weeks of enrollment. A bone marrow aspirate or biopsy confirming the suspected diagnosis will be documented in the electronic medical records. Bone marrow aspirate / biopsy documenting no evidence of leukemia will be performed after completion of therapy. Evaluations within 14 days of beginning therapy will include:

1. A history and physical exam, including a list of active medications
2. Hematologic studies: complete blood count with platelet and differential cell counts.
3. Chemistry panel (including electrolytes, creatinine, uric acid, albumin, total protein, calcium and phosphate)
4. Hepatic panel: serum SGOT, SGPT, alkaline phosphatase, total bilirubin, PT/PTT.
5. Reticulocyte count
6. An EKG

5. Treatment Plan

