5.1. Treatment Schedule

The planned initial dose of 5AC is $37.5\text{mg}/\text{m}^2$ (Level 0) and this will be administered subcutaneously or intravenously for days 1 through 5 of a 28 day cycle. Patients who tolerate the combination with no SAEs during two consecutive cycles will be eligible for a dose escalation to $50\text{mg}/\text{m}^2/\text{day}$ for 5 days of every 28 day cycle (Level +1). Patients who tolerate Dose Level +1 with no SAEs during two consecutive cycles will be eligible for a dose escalation to $75\text{mg}/\text{m}^2/\text{day}$ for 5 days of every 28 day cycle (Level +2). Patients will

continue at Dose Level +2 for the study’s duration provided there are no toxicities requiring dosing delays or dose reduction.

Dose reductions are permitted as per the standard treatment approach with 5AC and are listed below in Table 2. Patients who experience toxicity or dosing delays, but return to pre-therapy baseline within 56 days of the first day of their most recent cycle, will be eligible to continue at the next lower Dose Level (Table 2). Patients unable to tolerate the lowest dose of 12.5mg/m² /day for 5 days (Dose Level -2) due to toxicities or cytopenias, will be removed from the study. Patients requiring a dose reduction are not eligible for re-escalation. Azacitidine dosing is the same regardless of subject age.

Table 2

Dose Level	5AC
-2	12.5mg/m ²
-1	25mg/m ²
0	37.5mg/m² (starting dose level)
+1	50mg/m ²
+2	75mg/ m ²

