7.3. Timing of Initiation and Duration of Treatment

After SCT the majority of acute GVHD occurs within the first 60 days. To ensure patients are stable prior to initiating maintenance therapy, the study will start no sooner than after the day 60 post-transplant bone marrow biopsy results are available. As many relapses occur within the first several months,⁹ subjects must be enrolled within 185 days of transplant or chemotherapy. Treatment with 5AC and GM-CSF must then begin within 14 days of enrollment. Approximately half of relapses occur within the first year after SCT, with 80% occurring within the first two years.⁹ Accordingly, we would limit the duration of maintenance therapy to one year and follow patients for an additional two years.

7.4. 5-Azacytidine (NSC 102816)

1. Chemical Name: 4-Amino-1-β-D-ribofuranosyl-1,3,5-triazin-2(1H)-one
2. Other Names: 5-Azacytidine, 5-AZA, Mylosar7, Ladakamycin, Vidaza
3. Supply: 5AC is supplied as 100 mg of white, lyophilized powder with 100 mg of mannitol, USP in 30 ml flint vials. The contents of each vial should be dissolved in 4mL of sterile water or 0.9% sodium chloride to provide a 25 mg/ml slurry. 5AC does not go into solution but forms loose slurry when reconstituted in this fashion. *Do not inject the slurry intravenously.* Single injections should not exceed 2ml. Doses requiring larger volumes may be split into multiple injection

sites if volume to be administered is too large. Injection sites should be rotated on a daily basis.

4. **Storage and Stability:** Store un-reconstituted vials at 25 degrees C (77 degrees F); excursions permitted to 15-30 degrees C (59-86 degrees F) (See USP Controlled Room Temperature). 5AC reconstituted for subcutaneous administration may be stored for up to 1 hour at 25 degrees C (77 degrees F) or for up to 8 hours between 2-8 degrees C (36 and 46 degrees F). The constituted solutions hydrolyze at room temperature and should be used within 30 minutes for delivery of maximum potency.

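### Pregnancy is a mandatory treatment stop, but the only scheduled pregnancy test is before treatment: none is scheduled before cycles 2 to 12 or at End of Treatment

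*Combined protocol and SAP*

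**What the plan says.** All references are to the combined protocol and SAP.

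- **Consequences of pregnancy.** It is an exclusion (3.3, item 3), a reason to end treatment (5.3, item 9) and a listed SAE (10.5, item 7). Section 10.8 requires immediate discontinuation of 5AC, specialist referral and follow-up to the end of the pregnancy. It also makes pregnancies up to four weeks after the last dose reportable.
- **Testing.** Table 4 in 5.6 has one relevant row, "Serum HCG for applicable women only". It is marked under pre-treatment and blank under the weekly, Day 1 and End of Treatment columns. The footnote to the pre-treatment column reads "Within 14 days prior to enrollment". No other section schedules a pregnancy test.
- **Start of treatment.** Section 7.3 states: "Treatment with 5AC and GM-CSF must then begin within 14 days of enrollment". Section 4 (Pretreatment Plan) has a different clock, "Evaluations within 14 days of beginning therapy will include", followed by six items that do not name HCG.
- **Exposure.** 5AC is given "for days 1 through 5 of a 28 day cycle" (5.1) for 12 planned cycles, with Day 1 to Day 1 spacing of 28 to 56 days (5.3).
- **Other safeguards.** Inclusion criterion 9 requires effective barrier contraception. Table 4 schedules history and examination, toxicity recording and diary review on Day 1 of each cycle. Section 5.6 adds: "This represents the basic follow-up plan and this will change for a change in patient condition".

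**The concern.** The plan has a firm rule for what happens once a pregnancy is known, but after baseline it schedules no test that would make one known. A woman who conceives after the pre-treatment test can receive further 5AC courses until she or a clinician suspects pregnancy. Suspicion may come late, because the protocol's own list of common 5AC reactions (7.4, item 6) includes nausea (71%), vomiting (54%) and fatigue (36%), so early symptoms of pregnancy could be put down to the drug. Section 10.8 takes the hazard seriously enough to ask for reports of infant deaths suspected to follow exposure in utero. At stake is avoidable fetal exposure, not the validity of the trial's results.

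**Working it through.** The plan states no figure for test age or testing interval, so there is nothing to reproduce. The check adds the stated windows.

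**Scheduled tests**
- Before treatment: 1 (Table 4).
- On Day 1 of cycles 2 to 12: 0 of 11.
- At End of Treatment: 0.

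The column position of the single mark appears reliable. In the same table the reticulocyte row keeps its blank cells and shows a separate End of Treatment mark.

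**Maximum age of the test at first dose**
- Literal reading: (test to enrolment) + (enrolment to first dose) = 14 days (Table 4 footnote) + 14 days (7.3) = 28 days.
- If the Section 4 window is taken to cover all pre-treatment evaluations: 14 days.

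**Time from first dose to Day 1 of cycle 12 with no scheduled repeat**
- There are 12 − 1 = 11 cycle intervals.
- Shortest spacing: 11 × 28 = 308 days.
- Longest spacing allowed by 5.3: 11 × 56 = 616 days.

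**Effect of the proposed schedule**
- Added assays for a woman completing treatment: 12 (Day 1 of each cycle) + 1 (End of Treatment) = 13.
- Longest interval between scheduled on-treatment tests: one cycle, 28 to 56 days before the visit tolerance in 5.6.
- The first dose would follow a cycle 1 Day 1 result, whichever pre-treatment window governs.

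**The case against.** The strongest reply is that the plan is not silent. Contraception is mandatory, a clinician sees the patient on Day 1 of every cycle, and 5.6 lets the schedule change with the patient's condition, so a test on suspicion is always possible. Prior transplant or chemotherapy may also reduce fertility. All of this lowers the risk and should be credited. It does not supply detection: contraception reduces conception without revealing it, and the other measures need someone to suspect pregnancy first. Criterion 9 itself provides for fertile patients.

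A second reply concerns the 28 days, and part of it stands. Section 4 and the Table 4 footnote use different clocks. The Section 4 list also omits other pre-treatment items in Table 4, such as weight, performance status and magnesium, so it may be incomplete rather than deliberate in leaving out HCG. One work-up satisfying both windows would be at most 14 days old at first dose. The 28 days is therefore a literal maximum, not an expected value.

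Three further inferences are tempting, but the documents do not support them:
- **That the untested period is capped at one year.** Section 2.9 says "therefore we would limit the duration of maintenance therapy to one year" and 7.3 says "Accordingly, we would limit the duration of maintenance therapy to one year and follow patients for an additional two years". Both are statements of rationale. The operative spacing rule in 5.3 allows 616 days to Day 1 of cycle 12.
- **That the share of courses started without a new test measures risk.** It only restates one test for 12 cycles and assumes that all 12 are completed.
- **That pregnancies in partners of male patients are a demonstrated gap.** The unanticipated-problems policy cited in 10.7 extends to others besides participants, and the neonatal-death sentence in 10.8 is not limited to the subject. Consent pages are also absent from the text reviewed, so this cannot be judged.

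**Conclusion.** The point holds as a patient-safety gap in the assessment schedule and should be corrected. There is one scheduled HCG before treatment and none before cycles 2 to 12 or at End of Treatment. By Day 1 of cycle 12, 308 to 616 days have passed since first dose without a scheduled repeat. At first dose the single test is at most 28 days old on the literal reading, or 14 days if Section 4 governs.

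This rests on two assumptions: that Table 4 is the full testing schedule, and that the patient reaches cycle 12, since 5.3 lists many earlier stops. The documents give neither a conception rate nor the number of applicable women, so no count of pregnancies or exposures can be given. A reader might infer that exposures are likely, or that the trial's results are compromised. Neither follows: unscheduled testing is allowed and may well occur, and no endpoint, estimate, sample size or stopping boundary depends on this row of the table.

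**What to change.** In Table 4, keep the pre-treatment HCG for eligibility. Also mark HCG for applicable women on Day 1 of every cycle, including cycle 1, with the result known before 5AC is given, and at End of Treatment. Including cycle 1 settles the age of the test at first dose, so no separate addition to Section 4 is needed.

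The cost is a short amendment to one table row and at most 13 added assays per applicable woman. The complete blood count and metabolic panel are already scheduled at the same visits, so no extra visit or blood draw is needed. The drawback is an occasional false positive, which could briefly delay a cycle while it is repeated. The per-cycle interval is a judgement, since the documents set no testing standard. It is proposed because it places a result ahead of each new 5AC course.

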3.3. Exclusion Criteria

1. Patients with untreated or uncontrolled infections
2. Patients with untreated or uncontrolled grade 3 or 4 GVHD
3. Pregnancy and lactation
4. Concurrent use of any other investigational agents.
5. Known HIV-positive patients.
6. Known hypersensitivity to 5AC or GM-CSF

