10.8. Pregnancies

Pregnancies occurring while the subject is on 5AC or within 4 weeks after the subject's last dose are considered unanticipated reportable events. If the subject is on 5AC, it is to be discontinued immediately. The Investigator will follow the subject until completion of the pregnancy, and will provide any new information as a follow-up to the initial SAE. The subject should be referred to an obstetrician/gynecologist experienced in reproductive toxicity for further evaluation and counseling. All neonatal deaths that occur within 30 days of birth should be reported, without regard to causality, as unanticipated SAEs. In addition, any infant death after 30 days that the Investigator suspects is related to the *in utero* exposure to 5AC should also be reported.

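### The only required pregnancy test can be up to 28 days old at the first 5AC dose, because serum HCG is timed to enrolment and not to the start of treatment

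*Combined protocol and SAP*

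**What the plan says.** The timing of the pregnancy test has to be pieced together from three places in the combined protocol and SAP.

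- **Section 5.6, Table 4.** The row "Serum HCG for applicable women only" is marked in the pre-treatment column only. The footnote to that column reads "Within 14 days prior to enrollment".
- **Section 7.3.** This sets the gap between enrolment and first dose: "Treatment with 5AC and GM-CSF must then begin within 14 days of enrollment".
- **Section 4.** A list of baseline tests is tied to the start of treatment: "Evaluations within 14 days of beginning therapy will include". It covers history and physical with medications, blood count, chemistry, hepatic panel with PT/PTT, reticulocytes and EKG. HCG is not on it.

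Section 4 also times the history and physical to enrolment: "A complete history and physical examination and list of medications will be documented for each patient within two weeks of enrollment". That assessment therefore has two anchors, while HCG has only the enrolment one.

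Pregnancy appears in Section 3.3 as an exclusion ("Pregnancy and lactation"), in Section 5.3 as a reason to stop treatment ("Patient pregnancy") and in Section 10.5 as a serious adverse event by definition. Section 10.8 adds "If the subject is on 5AC, it is to be discontinued immediately" and asks for referral to a specialist in reproductive toxicity.

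**The concern.** The HCG test is there to keep a pregnant woman from receiving 5AC. What matters for that purpose is how old the result is on the day of the first dose, and the plan does not limit this directly. It limits the time from test to enrolment and, separately, the time from enrolment to treatment. The two windows add up. Nothing later in the schedule catches a pregnancy that the enrolment test missed or that began after it, apart from history and examination.

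The plan treats exposure in pregnancy as serious, yet it ties the EKG and the reticulocyte count to the start of treatment and leaves HCG out. No reason is given for the difference, which looks more like an omission than a decision. What is at stake is the safety of a few participants. The efficacy analysis is not involved.

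**Working it through.** The documents state no maximum age for the HCG result, so there is no figure of the plan's own to reproduce. The check adds the windows and then asks whether any other rule closes the gap.

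**Inputs**

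| Quantity | Value | Source |
|---|---|---|
| Test to enrolment, *a* | 0 to 14 days | Table 4 footnote |
| Enrolment to first dose, *b* | 0 to 14 days | Section 7.3 |
| Limit for tests timed to the start of treatment | 14 days | Section 4 |

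**Step 1: maximum age.** Age at first dose = *a* + *b*. The maximum is 14 + 14 = 28 days and the minimum is 0. For a test on the Section 4 list the maximum is 14 days.

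**Step 2: does another rule shorten this?** The 13 rows of Table 4 divide as follows.

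| Safeguard | Rows | Count |
|---|---|---|
| Section 4 list and Day 1 of each cycle | History/physical, blood count, metabolic panel, phosphate | 4 |
| Section 4 list only | PT/PTT, reticulocytes, EKG | 3 |
| Day 1 of each cycle only | Weight, performance status, magnesium, toxicity notation, diary | 5 |
| Neither | Serum HCG | 1 |

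4 + 3 + 5 + 1 = 13. HCG is the only row with nothing tying it to the start of treatment, and no other section asks for a pregnancy test closer to the first dose.

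**Step 3: how much of the permitted range exceeds 14 days?** In whole days, *a* and *b* each take 15 values (0 to 14), so there are 15 × 15 = 225 permitted pairs. Pairs with *a* + *b* ≤ 14 number 15 + 14 + … + 1 = 120. The remaining 225 − 120 = 105 give a test older than 14 days. This count shows only that the long intervals are not confined to one extreme corner. It is not a probability: it weights every pair equally, and the documents say nothing about the intervals expected in practice.

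**Step 4: sensitivity to the visit variation.** Section 5.6 allows ± 7 days for study visits other than weekly testing. Whether this covers the pre-treatment window is unclear. If it did, the maximum would be 28 + 7 = 35 days. The conclusion uses 28.

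**The case against.** The strongest reply is that 28 days needs an awkward workflow. Most baseline tests must satisfy both anchors, and PT/PTT, reticulocytes and EKG have no Day 1 repeat. A site will often draw one set of bloods that meets both windows. HCG drawn with that set is at most 14 days old at first dose. An older result arises only if HCG is taken separately and earlier, or if the other tests are repeated and HCG is left out. That is right, and it makes the long interval less likely. It does not exclude it, because a site that repeats exactly what Section 4 lists would leave HCG out.

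The Section 4 list is also not worded as exhaustive, so a site may test again. But being allowed to test is not the same as being required to.

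Third, Section 3.1 requires agreement to barrier contraception, and Table 4 has a history and physical on Day 1. Both lower the risk. The contraception agreement is for the duration of the study, so it does not clearly reach back to the days between test and enrolment, and a history is not a pregnancy test.

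Finally, Table 4 has no HCG in any of the 12 planned cycles, so the plan already relies on contraception and history for about a year. That is a fair reason to see this as a small point. The first dose still differs from later ones: it is where the exclusion in Section 3.3 takes effect, and a test already exists for that purpose.

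**Conclusion.** The concern holds. Under the stated windows, a serum HCG up to 28 days old at the first dose of 5AC is within the plan, twice the 14 days that Section 4 sets for other baseline tests. This rests on reading the Table 4 footnote and Section 7.3 as written, without the visit variation.

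The practical weight is small. The figure is a permitted maximum, a shared blood draw would usually keep the interval shorter, and only women for whom the test applies are affected; the documents do not say how many there will be. Two-year RFS, the sample size of 25 per arm and the futility and GVHD stopping rules are untouched. It is a worthwhile correction and not a serious defect.

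**What to change.** Keep the Table 4 footnote, so that pregnancy is still ruled out before enrolment. Add serum HCG for applicable women to the Section 4 list, and state that it is repeated before Cycle 1 Day 1 if the enrolment test will be more than 14 days old at first dose. One test that falls inside both windows satisfies both. The maximum age at first dose drops from 28 to 14 days, and none of the 105 longer timings reaches the first dose without a repeat. Testing in later cycles is a separate question and is not part of this change.

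The cost is one list item and an occasional HCG, which can be added to blood work already required before treatment. Moving the footnote's anchor for HCG from enrolment to first dose would also shorten the interval, but it would give up the check before enrolment.

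One consequence should be settled in the same edit. A woman with a positive repeat would be enrolled but not dosed. The futility looks in Sections 9.3 and 9.4 are triggered by numbers enrolled, and the off-study criteria in Section 3.5 do not mention pregnancy. A sentence should say whether she counts towards those numbers.
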